## G2. Data Analysis

Provide a description of your plan for data analysis. State the types of comparisons you plan (e.g. comparison of means, comparison of proportions, regressions, analysis of variance). Which is the PRIMARY comparison/analysis? How will the analyses proposed relate to the primary purposes of your study?

All analyses will be done on an intention-to-treat basis, indicating that all randomized participants and all outcomes will be included in the analysis according to their assigned treatment groups regardless of their adherence to their assigned treatment or their purported relationship to the treatment. Baseline Analysis: Imbalance in groups may occur by chance; we will examine baseline characteristics (e.g., age and psychotropic medication) of participants randomized to the two groups. Chi-square and t-tests will be used to evaluate the differences between groups for categorical and continuous variables, respectively.

Behavioral Outcome Analyses (Hypotheses 1-2). For all outcomes, we will examine the normality of the

distribution of the variable to determine if transformations such as log or inverse might be needed. In order to control for type I error due to multiple comparisons on multiple tests, we will use a rank sum scoring approach. There will be one rank sum score variable for the CAPS (primary outcome measure), and one for psychological tests (secondary outcome measures). The primary analysis is to assess the meditation effect, for which we will use a general linear mixed model, containing terms of treatment, time period, and interaction between time and treatment. The treatment effect will measure differences between the intervention and control groups at baseline, and the time effect will measure whether there was an overall change over time in the outcome. The term of most interest will be the interaction between time and treatment. A secondary analysis will include covariates of age and medication usage Method for Missing data: Because a research assistant verifies completion of each item, missing data are anticipated to be low. We assume any missing data will be missing at random, which can be indirectly verified by comparing the distribution of other important measures between patients with and without complete data. We will apply multiple imputation methods on the missing data and impute the missing data 20 times.

Functional Connectivity Processing and Analyses (Hyp 3). The Functional Connectivity Toolbox (Conn) within SPM8 implemented in Matlab (Mathworks Inc. Sherborn MA, USA) will process and analyze the FC data. Images will be realigned, coregistered, normalized in MNI space, and smoothed with a 6 mm FWHM Gaussian filter. Each subject's anatomical image will be segmented into gray and white matter (WM) and cerebrospinal fluid (CSF) masks. Physiological noise and movement will be addressed by using WM and CSF masks and realignment parameters as covariates. Data will be band-pass filtered at .008 - .01 Hz. Artifact Detection Toolbox ([nitrc.org/projects/artifact\\_detect/](http://nitrc.org/projects/artifact_detect/)) will repair artifact due to frame-by-frame head movement, i.e., scrub. WFUPickAtlas will create amygdala regions of interest (ROIs). GLM will estimate correlation between ROIs provided by Conn (e.g., ACC, PCC, MPFC), amygdala, and the whole brain in individual and group random effects analyses. Final T maps of between-groups t-tests will test the contrast, (Post\_IRV ? Post\_EC) MINUS (Pre\_IRV ? Pre\_EC) at the different seed regions. Reported clusters will be statistically significant ( $p=0.05$ , FWE) at the cluster level of inference, using Random Field Theory correction for multiple comparisons.

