## **Section D: Purpose and Objectives**

Aim. Investigate effects of a meditation intervention designed for Veterans (Inner Resources for Veterans; IRV) on three aspects of rehabilitation in Veterans with both mTBI and PTSD:

Hypothesis 1 (Rehabilitation of Community Integration and Quality of Life): Veterans participating in IRV, relative to an Education Control (EC) group, will exhibit improvements in community reintegration and quality of life after eight weeks of treatment.

Hypothesis 2 (Rehabilitation of Psychological Symptoms): Veterans participating in IRV, relative to an [(EC)] group, will exhibit improvements in PTSD and postconcussive symptoms after eight weeks of treatment.

Hypothesis 3 (Rehabilitation of Neural Networks): Following IRV, functional connectivity in the IRV group will be normalized, e.g., relative to the EC group, Veterans in the IRV group will demonstrate reduced Default Mode Network resting state functional connectivity with lateral prefrontal cortex (LPFC), and increased resting state functional connectivity between the rostral anterior cingulate and amygdala after eight weeks of treatment.

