## **Section F: Design/Procedure**

### **F1. Design**

Select one category that most adequately describes your research:

c) Pilot

Discuss the research design including but not limited to such issues as: probability of group assignment, potential for subject to be randomized to placebo group, use of control subjects, etc.

This is a prospective, randomized, controlled, single-blinded intervention study. Subjects will be randomized to either the IRV Meditation group or the Education Control group and have a 50% chance of being in either group.

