### Assessments

Pretreatment Assessment: Consented Veterans will then participate in a pretreatment assessment sessions that will consist of clinician administered and self-report instruments (e.g., the Structured Clinical Interview for DSM-IV Axis-I Disorders (SCID-I; Steiner et al., 1988; Shear et al, 2000); the Clinician-Administered PTSD Scale (CAPS; Blake et al., 1995; Weathers et al. 2001); the Beck Depression Inventory II (BDI-II; Beck et al., 1996); the PTSD Check List (Weathers et al., 1993); the Neurobehavioral Symptom Inventory (NSI), Trust Inventory, Trail-making task, and Rey Auditory Verbal Learning Test). Information on alcohol and drug use may be asked on the SCID or other form. These questionnaires will take approximately 2.5 hours for subjects to complete. Prior to beginning the interview, subjects will be informed that some of the questions are personal in nature, and that some of the questions may cause them to become upset, particularly PTSD participants when discussing their experiences. In addition, subjects will be reminded that they may take a break whenever necessary and can discontinue the questionnaires if they feel they need to.

Posttreatment Assessment: Approximately two weeks following the final treatment session, participants will complete a posttreatment assessment with a member of the study staff. The measures administered in this assessment will consist of those measures completed in the pretreatment assessment, with the addition of surveys designed to assess participants' therapy experience, e.g., the Client Satisfaction Questionnaire (CSQ).

Follow-up Assessment: Approximately eight weeks after the Posttreatment Assessment, participants will complete a Follow-up assessment with a member of the study staff. The measures administered in this assessment will consist of those measures completed in the pretreatment assessment.

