## Section G: Sample Size/Data Analysis

### G1. Sample Size

How many subjects (or specimens, or charts) will be used in this study?

Local: 60      Worldwide: 60

Please indicate why you chose the sample size proposed:

In a meditation study with Veterans that used mantra repetition, a component of IRV, reductions in Posttraumatic Stress Disorder Checklist total scores showed a moderate-to-large effect size, Cohen's  $d=0.72$  (0.2 is small, 0.5 is moderate, 0.8 is large). A study of loving kindness meditation with Veterans with PTSD reported a large effect size ( $d=0.89$ ) at a three month post-intervention follow-up. A third meditation study also with Veterans from other

war eras with PTSD showed large effect sizes on CAPS in both Intent to Treat (ITT) (Cohen's  $f=0.42$ , approx. equal to  $d=0.84$ ) and completer analyses ( $d=1.24$ ). We more conservatively assume an effect size of  $d=0.63$ . At a significance level of 0.05, with 40 patients (20 patients in each group) we will have power of 0.8 to detect the moderate to large effect size of 0.63. Assuming an attrition rate of 33%, 30 subjects are proposed in each group.

Functional Connectivity MRI Power Analysis (Hyp. 3). In the model that power analysis for fMRI SPM Random Effects Analysis was based on, brain signals are modeled by continuously distributed Gaussian kernels of random height and of width,  $f$ , in proportion to  $W$ , where  $W$  is the smoothness of the random field in units of voxels. Based on the pilot fcMRI data, with effect size of  $d = 0.70$ , observed  $W$  equivalent to [4.9 4.8 4.7] voxels FWHM, observed  $S = 2023$  resels, observed  $f = 2.72*W$ ,  $u = 3.167$ , calculated 2-tailed FWE-corrected cluster  $k_{\alpha}$

$(0.05) = 183$  voxels, shows that a power of 0.82 would be achieved by 20 subjects per group (after attrition). It should be also be noted that cluster sizes greater than this were observed in our fcMRI pilot data.

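### The NSI, the only listed postconcussive measure, has no test of its own, so the pooled secondary score cannot answer the postconcussive half of Hypothesis 2

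*Combined protocol and SAP*

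**What the plan says.** Hypothesis 2 in Section D has two halves. Veterans in the meditation arm (IRV), relative to the education control, "will exhibit improvements in PTSD and postconcussive symptoms after eight weeks of treatment".

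Section G2, under the heading for Hypotheses 1-2, uses rank sum scoring to limit type I error. "There will be one rank sum score variable for the CAPS (primary outcome measure"), and there is "one for psychological tests (secondary outcome measures"). Each score goes into a mixed model in which the time-by-treatment interaction is the term of interest. G2 does not list the components of the second score, gives no scoring directions, and provides no separate or follow-up test of any component.

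The Assessments part of F2 gives the battery as a list of examples. Besides the diagnostic interview and CAPS, it names the BDI-II (depression), the PTSD Check List (PCL), and "the Neurobehavioral Symptom Inventory (NSI), Trust Inventory, Trail-making task, and Rey Auditory Verbal Learning Test". The same measures are repeated at the posttreatment and follow-up assessments. No hypothesis in Section D mentions trust or cognition.

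**The concern.** CAPS covers the PTSD half of Hypothesis 2. For the postconcussive half, the only candidate is the NSI, and the only place it can enter the planned analysis is inside a pooled score. A rank sum depends on the total of its components' movements, not on which one moved. A significant score might come from depression or self-reported PTSD with the NSI unchanged. A null score might hide a real NSI effect. One of the trial's stated predictions would then end without an answer, although the data are collected at every assessment.

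The unlisted make-up adds a second problem. An equal-weight sum of the six measures named in the Assessments section would give half its weight to the Trust Inventory, Trail-making and verbal learning. If treatment does not move those three, they add mainly noise to this question.

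**Working it through.** **1. The plan's own figure.** Section G1 states: "At a significance level of 0.05, with 40 patients (20 patients in each group"), the trial has "power of 0.8 to detect the moderate to large effect size of 0.63". Allocation is equal: patients "have a 50% chance of being in either group" (F1). For a two-sample comparison the noncentrality is d × √(n/2) = 0.63 × √10 = 1.99. Two-sided t-test power at 5% is 49% (normal approximation 51%), so the stated 0.80 does not reproduce by this route. That is a separate issue. Here it means that the fair comparator for dilution is 49%, not 80%. The attrition step does reproduce: 20/(1 − 0.33) ≈ 30 ("Assuming an attrition rate of 33%, 30 subjects are proposed in each group").

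**2. Attribution.** This needs no arithmetic. Section D makes a postconcussive claim, and G2 offers CAPS and one pooled score. No planned result isolates the NSI.

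**3. Dilution, if the score has the six named parts.** For an equal-weight sum of k standardised components,

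d(score) = (sum of component effects) / √(sum of all entries of the correlation matrix).

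The documents give no correlations and no component effects. Assumed: 0.4-0.7 among BDI-II, PCL and NSI; 0.2-0.4 between the two cognitive tests; 0.1-0.2 for all other pairs; d = 0.63 on each component that responds; directions aligned; 20 per arm.

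- Low end of the correlations: 6 + 6 × 0.4 + 2 × 0.2 + 22 × 0.1 = 11.0. NSI-only effect 0.63/√11.0 = 0.190.
- High end: 6 + 6 × 0.7 + 2 × 0.4 + 22 × 0.2 = 15.4. NSI-only effect 0.63/√15.4 = 0.161.

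The rank sum itself was simulated: change scores ranked across both arms, ranks summed, two-sided t-test at 5%, counted when significant in favour of IRV. With no effect on any component the rate is about 2.5%.

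| Components that improve by 0.63 | Six-part score | Comparator |
|---|---|---|
| NSI only | 7-8% | about 49%, NSI alone (46-47% if ranked) |
| PCL and NSI | 15-20% | – |
| BDI-II and PCL, not NSI | 15-21% | – |
| BDI-II, PCL and NSI | 30-40% | 58-69%, three-scale symptom score |

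Rows two and three agree because the three symptom scales share one correlation in this model. The score sees two responding scales and cannot say which two.

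**4. Sensitivity of the NSI-only row** (two-sided t).

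- 4 to 8 components, common correlation 0 to 0.7, 20 per arm: from 0.63/√4 = 0.315, power 16%, down to 0.63/√(8 + 56 × 0.7) = 0.092, power 6%.
- Six components with 30 per arm: 7.5-16.5%, against 67% for the NSI alone.
- Effect rescaled so that a single scale truly has 80% power with 20 per arm: 8-21% for six components.

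**The case against.** The strongest reply concerns composition. G2 does not say that trust or cognitive tests are in the score, and the Assessments list is only a set of examples. Section D titles Hypothesis 2 as rehabilitation of psychological symptoms, so the score may be meant for symptom scales alone, in which case most of the dilution disappears. This stands. A reader might infer from the battery that the plan mixes in trust and cognition, but the documents do not establish it. What they establish is that the make-up is open. Nor is the count of six firm: the heading also covers Hypothesis 1, and a community integration instrument (CRIS-CAT) appears only in Section K.

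A reader might also conclude that the plan has about 7% power for postconcussive symptoms. It does not follow. That figure needs an NSI effect with none on the PCL or BDI-II, while Hypothesis 2 itself predicts PTSD improvement. Over the correlation structures examined, the six-part score with 20 per arm runs from about 6% (NSI only) to 66% (all three symptom scales improve, components uncorrelated).

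The simulated test is also simpler than the planned mixed model with multiple imputation in all randomised patients. The rows with 30 per arm and with the rescaled effect in step 4 show that the NSI-only gap remains.

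Finally, pooling protects type I error, the study is classed as a pilot, and a false lead is not frequent: when the NSI does not move but BDI-II and PCL do, the score is still non-significant in about 80% of trials. All fair. Yet Holm over two tests protects type I error too, and none of this supplies an answer on postconcussive symptoms.

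**Conclusion.** The attribution gap holds on the text alone and depends on no assumption: as written, no planned result can confirm or refute the postconcussive half of Hypothesis 2. The primary CAPS analysis is unaffected.

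The dilution is conditional on the trust and cognitive tests being in the score. On the assumptions above, it roughly halves power when all three symptom scales respond (30-40% against 58-69%) and leaves 7-8% against about 49% when only the NSI does. These are scenarios for judging the design of the score, not estimates of the plan's power. The 49% itself reflects the small sample, which this point does not cure.

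**What to change.** In G2:

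- Name the NSI total as its own secondary outcome for the postconcussive half of Hypothesis 2, analysed in the same mixed model.
- List the components of the secondary rank sum and the scoring direction of each.
- Limit that rank sum to symptom scales, and report the Trust Inventory, Trail-making and verbal learning results as exploratory. The exact make-up is partly a matter of preference: depression is in no hypothesis either, so keeping the BDI-II should be a stated choice.
- Apply Holm to the two secondary tests (NSI and symptom rank sum).

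The cost is wording plus one more secondary test; the measures are already collected. Holm has a price. If the NSI has the smaller p-value it is tested at 0.025, where its power at d = 0.63 with 20 per arm is about 38% rather than 49%. It is tested at 0.05 only if the rank sum has already passed.

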### Group Assignment

Following the assessment phase, participants will be randomized to either the IRV or EC group. The IRV intervention is a manualized meditation intervention that consists of eight 90-minute group sessions. The first third of each session is spent learning and practicing meditation techniques, the middle third on didactic material and group discussion, and the last third practicing meditation and debriefing. Outside of the sessions, subjects

practice approximately 30 minutes a day for 6 days per week. The Education Control group will cover material on PTSD (e.g., the causes, symptoms, and treatment) and will be held in sessions of similar duration.

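### The primary mixed model estimates a separate baseline CAPS mean in each arm although patients are randomised after baseline; a shared baseline mean would make the same contrast more precise using data already collected

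*Combined protocol and SAP*

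**What the plan says.** Section F1 says that patients "have a 50% chance of being in either group". The Assessments section places CAPS in the pretreatment session and repeats it at posttreatment (about two weeks after the last session) and at follow-up (about eight weeks later). The Group Assignment section fixes the order: "Following the assessment phase, participants will be randomized to either the IRV or EC group".

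Section G2 names the outcome: "There will be one rank sum score variable for the CAPS (primary outcome measure"). For the primary analysis, "we will use a general linear mixed model, containing terms of treatment, time period, and interaction between time and treatment". It then interprets the terms. On treatment: "The treatment effect will measure differences between the intervention and control groups at baseline". On the interaction: "The term of most interest will be the interaction between time and treatment". The only other behavioural model is described thus: "A secondary analysis will include covariates of age and medication usage". Baseline CAPS is not among its covariates.

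G2 analyses all randomised participants, with 20 multiple imputations. G1 plans 30 per arm with 33% attrition and states that "with 40 patients (20 patients in each group) we will have power of 0.8 to detect the moderate to large effect size of 0.63".

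**The concern.** Because allocation follows the baseline CAPS, the two arms have the same baseline mean in the population, and any observed difference is chance. G2 nevertheless spends a parameter on that difference. Its own interpretation of the treatment term rules out reading the model as already having a common baseline.

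The interaction is then a difference in change from baseline, which subtracts the whole baseline score. Unless the pre/post correlation is very high, that is more than the baseline predicts, so noise is carried into the contrast. With about 20 completers per arm, power is scarce, and the data needed to recover the precision are already being collected.

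**Working it through.** **Inputs.** From the documents: 1:1 allocation, 30 randomised and 20 completing per arm, alpha 0.05 (taken as two-sided; G1 does not say), d = 0.63. Assumed: rho of 0.3 to 0.9, d in raw-score SD, equal SDs at the visits, dropout before posttreatment.

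**1. The plan's own figure.** A two-sided t-test with 20 per group and d = 0.63 has noncentrality 0.63 × √(20/2) = 1.99 on 38 df, and power 0.49, not 0.80. Power close to 0.80 appears with 40 per group (0.795), or with a change score at rho of about 0.76. G1 mentions neither. The attrition arithmetic is right: 20/(1 − 0.33) ≈ 30.

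**2. Complete data.** In SD² units with n per arm, the variance of the posttreatment contrast is:

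- planned model (difference in mean change): 2 × 2(1 − rho)/n
- common baseline mean: 2 × (1 − rho²)/n
- ratio: (1 − rho²)/[2(1 − rho)] = (1 + rho)/2, that is 0.65, 0.75, 0.85 and 0.95 at rho 0.3, 0.5, 0.7 and 0.9.

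With three visits and equal correlations, the exact generalised least squares calculation gives the same posttreatment ratios at rho 0.3, 0.5 and 0.7, so the follow-up visit does not change them.

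**3. With the planned attrition.** Let N = 30 have a baseline and n = 20 a posttreatment score in each arm. The planned model already uses the dropouts' baselines:

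- planned: 2 × [(1 − rho²)/n + (1 − rho)²/N]
- common baseline: 2 × (1 − rho²)/n

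At rho 0.5 the planned variance is 2 × (0.75/20 + 0.25/30) = 0.0917, against 2 × 0.75/20 = 0.0750, a ratio of 0.82. Noncentrality is 0.63/√0.0917 = 2.08 against 0.63/√0.0750 = 2.30. Power below is by noncentral t on 38 df (planned) and 37 df (common), with the covariance treated as known.

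| rho | Variance, planned | Variance, common | Ratio | Power, planned | Power, common |
|---|---|---|---|---|---|
| 0.3 | 0.1237 | 0.0910 | 0.74 | 0.42 | 0.53 |
| 0.5 | 0.0917 | 0.0750 | 0.82 | 0.53 | 0.61 |
| 0.7 | 0.0570 | 0.0510 | 0.90 (0.895) | 0.73 | 0.78 |
| 0.9 | 0.0197 | 0.0190 | 0.97 | 0.992 | 0.994 |

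If dropout is spread out (30, 25 and 20 per arm at the three visits), the posttreatment ratio is 0.69, 0.78 and 0.87 at rho 0.3, 0.5 and 0.7.

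**4. Unequal SDs.** Entry requires PTSD on CAPS, which may narrow the baseline spread. With baseline SD s times the posttreatment SD, the complete-data ratio is (1 − rho²)/(1 + s² − 2·rho·s). At s = 0.8 it is 0.78, 0.89 and 0.98 at rho 0.3, 0.5 and 0.7. At s = 0.7 and rho 0.7 it is 1.00, so there is no gain. At s = 1.2 it is 0.53, 0.61 and 0.67. It never exceeds 1.

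**5. Validity and ranks.** In simulation with 20 complete pairs per arm, on raw scores and on pooled ranks, both approaches kept type I error between 0.046 and 0.055 and had essentially the same mean effect. G2 does not say how ranks are formed. Ranking within visit (assumed, complete data) gave power 0.34 to 0.50, 0.44 to 0.56 and 0.63 to 0.71 (0.715) at rho 0.3, 0.5 and 0.7, a gain similar to that on raw scores.

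**6. Does the remedy do what it should?** With visit as a factor, the full model has 6 mean parameters. A formula with time and time-by-treatment but no treatment main effect still has rank 6 and spans the same space, because the software keeps a baseline treatment column. Omitting that column gives rank 5, which is the constraint wanted. In one simulated trial (rho 0.5), adding baseline as a covariate while it stayed a response left the interaction estimate at 0.501. The common-baseline model gave 0.399, and baseline as a covariate only gave 0.400.

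**The case against.** The planned model is standard and unbiased, and F1 calls the study a pilot. That is fair, and it makes this an improvement rather than the correction of an error. A reader might infer that the planned contrast is biased by chance baseline imbalance. It is not: over repeated randomisations the imbalance averages to zero.

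A reader might also quote the complete-data gain, such as 0.38 to 0.53 at rho 0.3. That compares 20 complete pairs per arm, whereas G2 analyses everyone randomised, and the dropouts' baselines already help the planned model. The complete-data power gain is about a quarter to a third smaller once the planned attrition is allowed for.

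It is also tempting to say that G1's 0.80 implies rho of about 0.76, and to size the gain there (0.82 to 0.85 with attrition). G1 mentions no correlation or change score, other inputs also give about 0.80, and the value depends on an unstated standardiser. If d were in change-score SD, complete-data planned power would be 0.49 at every rho, rising to 0.54 at rho 0.76.

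Two neighbouring matters are not part of this point. Three visits make the interaction more than one contrast, but Section D already points to the effect after eight weeks of treatment, so naming the visit is a clarification. Both arms are delivered in groups, so outcomes within a therapy group may be correlated. The effect of that on type I error depends on group numbers, group sizes and an intraclass correlation that the documents do not give. The word unbiased here therefore covers baseline handling only and is not a general clearance of the analysis.

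**Conclusion.** The point holds as a loss of precision. By the plan's own account baseline CAPS is free to differ by arm, and nothing in the behavioural analyses uses it as a covariate. Under equal variances, d in raw-score SD and all attrition before posttreatment, the common baseline removes about 26%, 18% and 10% of the contrast variance at rho 0.3, 0.5 and 0.7. That is worth roughly 0.11, 0.08 and 0.05 of power before the small cost of estimating the baseline slope. The direction is certain under randomisation after baseline. The size is not, because rho, the standardiser and the SDs are not in the documents. The change should be made, but the plan is not invalid without it.

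**What to change.** In G2, replace the primary model with a constrained longitudinal model: visit effects, one baseline mean shared by both arms, and treatment-by-visit terms for posttreatment and follow-up only. Say explicitly that the baseline-by-treatment column is omitted, or that both arms are coded alike at baseline. Deleting the treatment main effect from a factor-coded formula does not impose the constraint.

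The alternative is to take baseline out of the response and enter baseline CAPS as a covariate. If a rank score is analysed, use the same rank score at baseline. Adding baseline as a covariate while it remains a response does not help. The multiple-imputation model should be made consistent with the chosen analysis: baseline CAPS and arm included, and the same scale used.

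The cost is negligible: a wording change with no new data, visits or patients. In complete-data simulation, estimating the baseline slope lowered power by about 0.01 (0.522, 0.598 and 0.764 at rho 0.3, 0.5 and 0.7, against 0.530, 0.611 and 0.775 by formula).

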## **F2. Procedure**

### Overall

Subjects will attend consent and assessment visits prior to being placed in the Inner Resources for Veterans (IRV) meditation intervention or education control (EC) groups. Before beginning the group and group completion, subjects will also undergo MRI.

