## **Section R: Advertisements**

### **Mode of Advertising: Newspaper**

Exact language of Advertisement:

Meditation Therapy for the Treatment of PTSD and mTBI using Functional MRI 8 week research study with compensation

Eligibility: • OEF/OIF/OND Veterans • Diagnosis of PTSD & Mild Traumatic Brain Injury • Between 18-49 years old • No current serious medical conditions • Free from metal in body • Not claustrophobic • Enrolled in or willing to be enrolled in VA

Requirements of program: • Screening • Pre & post treatment assessments and MRI brain scans • 8-week meditation or PTSD education group

Possible benefits: • Practice relaxed alertness • Reduce PTSD symptoms • Improve sleep, decrease pain, reduce depression & anxiety

Compensation up to \$110 and receive images of your brain!

Study Coordinator

[name] [contact] [name]

Study is funded by the Department of Veterans Affairs—Rehabilitation Research & Development Service

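### IRV, and apparently EC, is delivered in therapy groups, but the primary model and the power figure make no allowance for correlated change within a group

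*Combined protocol and SAP*

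**What the plan says.** F1 (Design) describes individual 1:1 randomisation and labels the study a pilot. Group Assignment states the IRV format outright: "The IRV intervention is a manualized meditation intervention that consists of eight 90-minute group sessions". A third of each session is didactic teaching and discussion among members.

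For EC, the same section gives the topics and says only that it "will be held in sessions of similar duration". Two other places point to group delivery. The Overall paragraph of F2 says of all subjects: "Before beginning the group and group completion, subjects will also undergo MRI". All five advertisements in Section R offer an "8-week meditation or PTSD education group".

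The primary model in G2 reads: "we will use a general linear mixed model, containing terms of treatment, time period, and interaction between time and treatment". The interaction is the term of most interest, and a secondary analysis adds age and medication. No random effect is named for participant, therapist or therapy group. G1 states that "with 40 patients (20 patients in each group) we will have power of 0.8" at d = 0.63 and a 0.05 significance level, then raises 20 to 30 per arm for 33% attrition. No design effect, ICC, group size or number of groups appears anywhere.

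**The concern.** Members of one therapy group share a leader, peers and discussion. Their outcomes may therefore move together even though each person was randomised separately. The groups form after baseline, so the correlation that matters is in change, which is what the interaction measures. A participant random effect, had it been named, would handle repeated measures on one person. It would not absorb a shift shared by everyone in the same therapy group.

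If such a shift exists and the model omits it, the interaction's standard error is too small, its interval too narrow and its false-positive rate above 5%. The rank-sum scoring in G2 is aimed at multiple outcomes and does not address this.

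**Working it through.** **The plan's own figure.** For a two-sided, two-sample t-test with independent observations, n = 20 per arm and d = 0.63, the noncentrality is 0.63 × √(20/2) = 1.99 on 38 df, and power is 0.49 (0.62 one-sided). The stated 0.80 is not reproduced this way; 40 per arm would give 0.795. It could be reached with an unstated baseline-to-post correlation of about 0.72 (covariance adjustment) or 0.76 (change score). That is a separate matter. What counts here is that none of the variants tried contains an allowance for clustering. The attrition step does reproduce: 20/(1 − 0.33) = 29.9, so 30.

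**Inputs.** From the documents: 20 analysed per arm, alpha 0.05, d = 0.63, interaction as target. Assumed, because the documents are silent: two-sided testing; 5, 4, 3 or 2 groups per arm (m = 4, 5, about 6.7 or 10 analysed members); ICC of change 0, 0.02, 0.05, 0.10.

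**Formulas.** Design effect DE = 1 + (m − 1) × ICC. If both arms cluster, the true variance of the treatment difference is DE times the modelled variance. If only IRV clusters, the factor is (1 + DE)/2. With variance factor V, the approximate false-positive rate is 2 × [1 − Φ(1.96/√V)].

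Example with m = 10 and ICC 0.05: DE = 1 + 9 × 0.05 = 1.45.
- Both arms: 1.96/√1.45 = 1.628, giving 10.4%.
- IRV only: V = 2.45/2 = 1.225, 1.96/√1.225 = 1.771, giving 7.7%.

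**Simulation.** False-positive rate (%) of an independent t-test on change, 100,000 runs per cell, for 5 / 4 / 3 / 2 groups per arm:

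| ICC of change | Both arms clustered | Only IRV clustered |
|---|---|---|
| 0 | 5.2 / 5.0 / 4.9 / 4.9 | – |
| 0.02 | 5.7 / 6.0 / 6.3 / 7.2 | 5.3 / 5.5 / 5.7 / 6.0 |
| 0.05 | 6.9 / 7.4 / 8.3 / 10.5 | 5.9 / 6.1 / 6.7 / 7.7 |
| 0.10 | 8.6 / 9.8 / 12.1 / 16.1 | 6.9 / 7.4 / 8.6 / 10.5 |

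**Closer to the stated plan.**
- Three-visit interaction F-test with a participant intercept: 5.6-16.1% over ICC 0.02-0.10 with both arms clustered, 5.3-10.8% with IRV only.
- The same test on ranks within visit (one reading of the rank score), both arms, ICC 0.05: 6.5-9.4%.
- 30 per arm with 10 missing and 20 imputations without a group term: 5.5-16.2% over ICC 0.02-0.10 with both arms clustered, 4.9-10.4% with IRV only.

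**Information.** At ICC 0.05, DE runs from 1 + 3 × 0.05 = 1.15 to 1.45. Forty completers then carry the information of 40/1.15 = 34.8 down to 40/1.45 = 27.6 independent ones.

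**A group-adjusted test.** A t-test on therapy-group mean change with g groups per arm has standard error √{(2/g) × [ICC + (1 − ICC)/m]} in SD units of change, on 2g − 2 df. For g = 5, m = 4 and ICC 0.05 this is √(0.4 × 0.2875) = 0.339, and the noncentrality is 0.63/0.339 = 1.86. For 5 / 4 / 3 / 2 groups per arm:
- Critical t is 2.31 / 2.45 / 2.78 / 4.30, against 2.02 for the unadjusted test.
- Power at ICC 0.05 is about 0.37 / 0.33 / 0.27 / 0.17.
- Power at ICC 0 is about 0.42 / 0.39 / 0.33 / 0.22, against 0.49 unadjusted.
- Simulated size is 4.8-5.2% throughout, with complete data.

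**The case against.** The strongest reply is that G2 leaves the random effects unstated and does not exclude a group effect. It calls the analysis a mixed model and names only the fixed terms, in a short description on an institutional form for a pilot. That is fair, and a reader should not infer that the plan rules out a therapy-group effect. It remains true that fitting the terms as listed ignores the groups, and the structure can be settled only before outcomes are seen.

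Second, the magnitude is entirely assumed. A reader might infer that this trial's error rate is 16%. The documents do not support that. The figure needs ICC 0.10, clustering in both arms and two groups per arm. With one-third attrition, 10 analysed members means about 15 assigned to each group (10 ÷ 2/3), and nothing in the documents suggests groups that large. At ICC 0.02 with only IRV clustered, the excess is under about one percentage point.

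Third, group delivery of EC is inferred. Elsewhere in the document the word group also means the treatment arm, so the Overall sentence is weak evidence; the advertisements are better. The larger figures depend on that inference.

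Fourth, a companion analysis leaves the primary test unadjusted, and with few groups it will often miss a real effect. This stands. The companion shows how far a claim depends on treating group members as independent; it does not repair the primary test.

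**Conclusion.** The point holds as a cheap improvement. Group delivery is stated for IRV and apparent for EC, and neither the primary model nor the power figure allows for it. If change correlates within therapy groups, the interaction is reported with too much precision. Under the assumed values a nominal 5% test runs at about 5.3-10.5% if only IRV clusters and about 5.5-16% if both arms do; with no correlation it stays at about 5%.

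Two stronger readings are not supported. The documents do not show that the primary result will be invalid, because they contain no ICC. The gap between the stated power of 0.80 and the 0.49 from a plain two-sample calculation is not caused by clustering, since the 0.49 already assumes independent participants.

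**What to change.** 1. Record the assigned therapy-group ID for every randomised participant, including early leavers. State the planned number and size of groups per arm, and whether EC meets in groups.
2. In G2, name the participant random effect. Beside the stated primary model, pre-specify one group-adjusted analysis of the interaction before outcomes are seen.
   - If both arms meet in groups: a t-test on therapy-group mean change from baseline to the posttreatment assessment. Hypothesis 2 says participants "will exhibit improvements in PTSD and postconcussive symptoms after eight weeks of treatment", and the nearest planned visit is this one: "Approximately two weeks following the final treatment session, participants will complete a posttreatment assessment".
   - If only IRV does: a partially nested model with a random therapy-group effect in IRV only and Satterthwaite or Kenward-Roger degrees of freedom, noting that error control is approximate with 2 or 3 groups.
3. Include therapy group in the multiple imputation that feeds this analysis.
4. With any claim of effect, report the group-adjusted estimate and interval and say whether the conclusion holds. With few groups, treat non-significance as imprecision and not as refutation.
5. In G1, state that the power figure assumes no clustering.

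The cost is one recorded field and one added analysis; the primary model is unchanged. Where both arms meet in groups, the group-adjusted interval is on average 1.2 / 1.3 / 1.5 / 2.3 times as wide as the unadjusted one with 5 / 4 / 3 / 2 groups per arm at ICC 0.05, and 1.1 / 1.2 / 1.3 / 1.9 times as wide at ICC 0. With the low power shown above, this is why the analysis belongs beside the primary model in a pilot.
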